10.2 DEFINITION OF SOURCE DATA

The results of certain examinations or evaluations recorded in the e-CRF may be considered source data:

- Patient's medical record,
- Local laboratory results including blood smear results.

10.3 HANDLING OF PATIENT STUDY DISCONTINUATION

Due to the mode of administration of IMP (FQ [capsules or suspension] followed by OZ439 suspension) and the dose regimen (single dose), the following may not apply (see [Section 8.1](#) for IMP administration).

10.3.1 Temporary treatment discontinuation with investigational medicinal products

Temporary treatment discontinuation after incomplete treatment (suspension ingestion) may be considered by the Investigator because of suspected AEs. Re-initiation of treatment with the IMP will be done under close and appropriate clinical/and or laboratory monitoring once the Investigator will have considered according to his/her best medical judgment that the responsibility of the IMP(s) in the occurrence of the concerned event was unlikely.

10.3.2 Permanent treatment discontinuation with investigational medicinal products

Permanent treatment discontinuation is any treatment discontinuation associated with the definitive decision from the Investigator or the patient not to re-expose the patient to the IMP at any time after incomplete treatment (suspension ingestion).

10.3.3 List of criteria for permanent treatment discontinuation

The patients may withdraw from treatment with the IMP if they decide to do so, at any time and irrespective of the reason, or this may be the Investigator's decision. All efforts should be made to document the reasons for treatment discontinuation.

10.3.4 Handling of patients after permanent treatment discontinuation

Patients will be followed-up according to the study procedures as specified in this protocol up to the scheduled date of study completion, or up to recovery or stabilization of any AE to be followed-up as specified in this protocol, whichever comes last.

10.3.5 Procedure and consequence for patient withdrawal from study

The patients may withdraw from the study before study completion if they decide to do so, at any time and irrespective of the reason:

If possible, the patients are assessed using the procedure normally planned for the end-of-study visit including a pharmacokinetics sample.

For patients who fail to return to the site, the Investigator should make the best effort to recontact the patient (eg, contacting patient's family or private physician, reviewing available registries or health care databases), and to determine his/her health status, including at least his/her vital status at the planned D63 date. Attempts to contact such patients must be documented in the patient's records (eg, times and dates of attempted telephone contact, receipt for sending a registered letter). The statistical analysis plan will specify how these patients lost to follow-up for their primary endpoints will be considered.

Patients who have withdrawn from the study cannot be re-randomized (treated) in the study. Their inclusion and treatment numbers must not be reused.

10.4 OBLIGATION OF THE INVESTIGATOR REGARDING SAFETY REPORTING

10.4.1 Definitions of adverse events

10.4.1.1 Adverse event

An **adverse event** (AE) is any untoward medical occurrence in a patient or clinical investigation patient administered a pharmaceutical product and which does not necessarily have to have a causal relationship with this treatment.

10.4.1.2 Serious adverse event

A **serious adverse event** (SAE) is any untoward medical occurrence that at any dose:

- Results in death, or
- Is life-threatening, or

Note: The term “life-threatening” in the definition of “serious” refers to an event in which the patient was at risk of death at the time of the event; it does not refer to an event which hypothetically might have caused death if it were more severe.

- Requires inpatient hospitalization or prolongation of existing hospitalization, or
- Results in persistent or significant disability/incapacity, or
- Is a congenital anomaly/birth defect
- Is a medically important event

Medical and scientific judgment should be exercised in deciding whether expedited reporting is appropriate in other situations, such as important medical events that may not be immediately life-threatening or result in death or hospitalization but may jeopardize the patient or may require medical or surgical intervention (ie, specific measures or corrective treatment) to prevent one of the other outcomes listed in the definition above.

Note: The following list of medically important events is intended to serve as a guideline for determining which condition has to be considered as a medically important event. The list is not intended to be exhaustive:

- Intensive treatment in an emergency room or at home for:
- Allergic bronchospasm
- Blood dyscrasias (ie, agranulocytosis, aplastic anemia, bone marrow aplasia, myelodysplasia, pancytopenia, etc),
- Convulsions (seizures, epilepsy, epileptic fit, absence, etc).
- Development of drug dependence or drug abuse
- ALT >3 x ULN + total bilirubin >2 x ULN or asymptomatic ALT increase >10 x ULN
- Suicide attempt or any event suggestive of suicidality
- Syncope, loss of consciousness (except if documented as a consequence of blood sampling)
- Bullous cutaneous eruptions
- Cancers diagnosed during the study or aggravated during the study (only if judged unusual/significant by the Investigators in oncology studies)
- Chronic neurodegenerative diseases (newly diagnosed) or aggravated during the study (only if judged unusual/significant by the Investigators in studies assessing specifically the effect of a study drug on these diseases).

10.4.1.3 Adverse event of special interest

Adverse event of special interest (AESI) is an AE (serious or non-serious) of scientific and medical concern specific to the Sponsor's product or program, for which ongoing monitoring and immediate notification by the Investigator to the Sponsor is required. Such events may require further investigation in order to characterize and understand them. Adverse events of special interest may be added or removed during a study by protocol amendment.

- Pregnancy occurring in a female patient entered in the clinical trial or in a female partner of a male patient entered in the clinical trial. It will be qualified as an SAE only if it fulfills one of the seriousness criteria (see [Section 10.4.1.2](#)).
- Follow-up of the pregnancy in a female participant or in a female partner of a male participant is mandatory until the outcome has been determined.
- Symptomatic overdose (serious or non-serious) with IMP
 - An overdose (accidental or intentional) with the IMP is an event suspected by the Investigator or spontaneously notified by the patient (not based on systematic pills count) and defined as at least twice the intended dose within the intended therapeutic interval, adjusted according to the tested drug.

Of note, asymptomatic overdose has to be reported as a standard AE.

10.4.1.4 Project specific AESIs

Owing to safety findings for FQ and OZ439 on ECG and hepatic parameters, an appropriate ECG and hepatic monitoring is proposed (see study flowchart, [Table 1](#)).

- Increase in alanine transaminase (ALT): ALT ≥ 3 ULN (if baseline ALT <ULN) or, ALT ≥ 2 times the baseline value (if baseline ALT \geq ULN) will be reported as AESI.

Cases of ALT >3 ULN will be monitored according to the procedures indicated in [Appendix D](#).

Patients with abnormal ALT values at D63 will be followed-up until ALT returns to normal values. A PK sample will be made at time of event for OZ439 and FQ (& SSR97213) concentration measurement.

An ALT increase >3ULN is reportable as an SAE in any of the following situation:

- Possible Hy's law (ALT or AST >3x upper limit of normal (ULN) and bilirubin >2x ULN and (>35% direct bilirubin) in the absence of a serum alkaline phosphatase level >2x ULN. [If fractionation is unavailable, record presence of detectable urinary bilirubin on dipstick indicating direct bilirubin elevations and suggesting liver injury] or
- When ALT >10 x ULN,
- When associated with jaundice or,
- When associated with coagulation disorder (PT<50%) or,
- In presence of signs of hepatic encephalopathy.

- QTcF ≥ 500 ms or QTcF prolongation >60 ms from baseline

In the event of QTcF interval ≥ 500 ms (automatic measurement) or a QTcF prolongation >60 ms (automatic measurement) from baseline, the patient should be placed under supervision in a specialized setting.

Subsequent ECG monitoring of the patient should then be performed on a regular and clinically responsible basis until the QTc interval returns to their baseline QTcF value.

In case of QTcF ≥ 500 ms (automatic measurement) or QTcF prolongation >60 ms from baseline, patient will have blood drawn for measurement of OZ439 and FQ (& SSR97213) concentration.

The Investigator will report an AESI only if QTcF ≥ 500 ms or QTcF prolongation >60 ms from baseline is confirmed by central reading.

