8.1.1 Ferroquine (FQ)

A combination of the following capsules will be used to compose the 4 doses; individual sachets containing sucrose granules are provided:

- 5 mg, 30 mg, 100 mg and 200 mg FQ or matching placebo.
- Placebo capsules are used to keep the same number of capsules in each weight band while keeping the FQ dose blinded. No patient will receive placebo only.
- For young children, capsules will be opened and their content will be diluted in water with sucrose granules in order to make it palatable and given as suspension.
- Oral route.
- Patients should have fasted from food and milk for 3 hours before administration. Neither food nor milk should be taken within 2 hour after the end of IMP dosing.
- Treatment duration: single dose at V2 Day 0.

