- Vital signs including BP and HR at each visit from V7-D7 to V15-D63 (except V10 and V12).
- Weight at V15-D63 only.
- Clinical laboratory safety: at V7-D7, V9-D14, V11-D21 and V13-D28 for patients >5 years (Cohorts 1 & 2).
- Clinical laboratory safety: at V7-D7, V9-D14 and V13-D28 for patients ≤5 years (Cohorts 3&4).
- Pregnancy test (for women of childbearing potential) at V13-D28 and V15-D63.
- IVRS/IWRS call for end of study (EOS).
- OZ439 PK sampling (see [Table 1](#)).
- FQ/SSR97213 PK sampling (see [Table 1](#)).
- PK samples for measuring FQ and SSR97213 concentrations at Post D7 first recurrence of parasitemia.

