11.4.4 Analyses of safety data

The summary of safety results will be presented by treatment arm thanks to descriptive statistics (summary tables, graphics) in the following way:

- Summary tables provided separately for “higher NAI” (African patients >5 years) and “lower NAI” populations, and within the “lower NAI” population, separately for African patients ≤ 5 years and Asian patients, by treatment arm, whatever the cohort.
- A summary table provided for “higher NAI population” by treatment arm and by cohort (Cohort 1 & 2).
- A summary table provided for “lower NAI population” by treatment arm and by cohort (Cohort 3 & 4).

No formal inferential testing will be performed.

All the safety analyses will be performed using the safety population.

For all safety data (see [Section 9.2.2.1](#) for details), the observation period will be divided into three phases:

- The pre-treatment phase defined as the time between the patient gives informed consent and the start time of first double-blind IMP administration (excluded).
- The on-treatment phase defined as the start time of first dose of double-blind IMP administration (included) up to Day 63 visit (included).
- The post-treatment phase will be defined as the time after the Day 63 visit (excluded).

For laboratory, vital signs and ECG parameters, Potentially Clinically Significant Abnormalities (PCSAs) will be analyzed using the last available version of PCSA list before database lock.

The following definitions will be applied to laboratory parameters, vital signs and ECG:

- The potentially clinically significant abnormality (PCSA) values are defined as abnormal values considered medically important by the Sponsor according to predefined criteria/thresholds based on literature review and defined by the Sponsor for clinical laboratory tests, vital signs and ECG.
- PCSA criteria will determine which patients had at least 1 PCSA during the on-treatment phase, taking into account all evaluations performed during the on-treatment phase, including unscheduled or repeated evaluations. The number of all such patients will be the numerator for the PCSA percentage.

Baseline safety parameters

The baseline value is defined as the last available value before first double-blind IMP at Visit 1 (Day-1) for laboratory, vital sign and Visit 2 (Day 0 before IMP administration) for ECG parameters. For ECG parameters, baseline will be the mean of the 3 consecutive measures (triplicate) done before dosing.

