Baseline definitions specific to each type of safety parameter will be detailed in corresponding sections.

Baseline safety data will be presented along with subsequent safety values assessed during or after dosing.

Drug-induced liver injury

The liver function tests, namely ALT, AST, alkaline phosphatase and total bilirubin, are used to assess possible drug induced liver toxicity. The proportion of patients with PCSA values at any post baseline visit by baseline status will be displayed by treatment arm for each parameter.

A graph of distribution (e-Dish plot) of peak values of ALT versus peak values of total bilirubin will be presented. Note that the ALT and total bilirubin values are presented on a logarithmic

scale. The graph will be divided into 4 quadrants with a vertical line corresponding to 3 x ULN for ALT and a horizontal line corresponding to 2 x ULN for total bilirubin.

The normalization (to ≤ 1 x ULN or return to baseline) of elevated liver function tests will be summarized by categories of elevation (3 x ULN, 5 x ULN, 10 x ULN, 20 x ULN for ALT and AST, 1.5 x ULN for alkaline phosphatase, and 1.5 x ULN and 2 x ULN for total bilirubin), with the following categories of normalization: never normalized, normalized after permanent discontinuation of study drug. Note that a patient will be counted only under the maximum elevation category.

The incidence of liver-related AEs will be summarized by treatment arm. The selection of preferred terms will be based on standardized MedDRA query (SMQ) Hepatic disorder. Time to liver-related treatment discontinuation and time to liver death may also be provided based on hepatic disorder SMQ.

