 - Anti-HAV IgM, anti-HBc IgM, (HBV-DNA if clinically indicated), anti-HCV and HCV RNA, anti-CMV IgM and anti-HEV IgM antibodies
 - Depending on the clinical context, check for recent infection with EBV, herpes viruses, and toxoplasma
 - Hepatobiliary ultrasonography (or other imaging investigations if needed)
 5. **CONSIDER** Auto-antibodies: antinuclear, anti-DNA, anti-smooth muscle, anti-LKM
 6. **CONSIDER** consulting with hepatologist
 7. **CONSIDER** patient hospitalization if INR > 2 (or PT < 50%) and/or central nervous system disturbances suggesting hepatic encephalopathy
 8. **MONITOR LFTs after discontinuation of IMP:**
 - As closely as possible (or every 48 hours) until stabilization, then every 2 weeks until return to normal/baseline or clinical resolution.
 9. **FREEZE** serum sample (Sml x 2)
 10. **In case of SUSPICION of GILBERT Syndrome**, a DNA diagnostic test should be done

[figure not shown]
Note:
 Normalization is defined as < ULN or baseline value if baseline value is >ULN.
 As soon as seriousness criterion is met or the event leads to permanent treatment discontinuation, the monitoring team should be notified within 24 hours.
 *If unable to retest in 72 hours, use original lab results to decide on further monitoring/ discontinuation .

NOTE: ALT ≥3 ULN (IF BASELINE ALT <LN) OR ALT ≥2 TIMES THE BASELINE VALUE (IF BASELINE ALT ≥ULN) SHOULD BE NOTIFIED WITHIN 24 HOURS TO THE MONITORING TEAM (SEE SECTION 10.4.1.4, SECTION 10.4.5).

IN ADDITION, IF ALT < 3 ULN MEETS A SERIOUSNESS CRITERION, THE EVENT SHOULD BE NOTIFIED WITHIN 24 HOURS TO THE MONITORING TEAM.

Due to single dose regimen, instructions regarding IMP discontinuation/resumption do not apply.

[figure not shown]
ACUTE RENAL FAILURE

Acute renal failure is to be recorded as AE only if at least one of the criteria listed in Section 10.4.3 is met. Acute renal failure is to be recorded as AE only if at least one of the criteria listed in the General guidelines for reporting adverse events in Section 10.4.2 is met.

Due to single dose regimen, instructions regarding IMP discontinuation/resumption do not apply.

SUSPICION OF RHABDOMYOLYSIS

Suspicion of rhabdomyolysis is to be recorded as AE only if at least one of the criteria listed in Section 10.4.3

Suspicion of rhabdomyolysis is to be recorded as AE only if at least one of the criteria listed in the General guidelines for reporting adverse events in Section 10.4.2 is met.

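### The ALT follow-up rule acts on a Day 63 value that no cohort has scheduled, and the liver-test recovery table has no class for a patient who normalises after a completed single dose

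*Protocol*

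**What the plan says.** Section 10.4.1.4 makes an ALT increase a project-specific AESI. The threshold is at least 3 ULN if baseline is below ULN, or at least twice baseline if baseline is at or above ULN. Cases above 3 ULN are sent to Appendix D. The section then adds: "Patients with abnormal ALT values at D63 will be followed-up until ALT returns to normal values".

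Section 10.1.6 sets the scheduled laboratory tests after discharge. For older patients: "Clinical laboratory safety: at V7-D7, V9-D14, V11-D21 and V13-D28 for patients >5 years (Cohorts 1 & 2". For young children: "Clinical laboratory safety: at V7-D7, V9-D14 and V13-D28 for patients ≤5 years (Cohorts 3&4". It lists no laboratory safety tests at Day 42 or Day 63.

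Section 11.4.4 defines one safety window for all data: "The on-treatment phase defined as the start time of first dose of double-blind IMP administration (included) up to Day 63 visit (included". Under drug-induced liver injury it tabulates recovery of elevated liver tests "with the following categories of normalization: never normalized, normalized after permanent discontinuation of study drug". Recovery means at or below 1 x ULN, or back to baseline.

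On dosing, Section 8.1.1 states "Treatment duration: single dose at V2 Day 0". Section 10.3.2 defines permanent discontinuation only for a dose that was not completed. Appendix D states: "Due to single dose regimen, instructions regarding IMP discontinuation/resumption do not apply".

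**The concern.** Two stated provisions do not fit the rest of the protocol.

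First, a follow-up rule is keyed to a visit at which the quantity it needs is not scheduled. A site that follows the schedule exactly has no Day 63 ALT on which to apply it.

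Second, the recovery table borrows a class from trials with continuing treatment. In a single-dose trial the favourable outcome, an elevated test that comes back to normal after a full dose, has nowhere to go.

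Both matter because Section 4.1 names elevated liver enzymes as an identified risk of each drug, alone or combined, and Section 4.2.2 says the study is to select a safe and efficacious dose for Phase 3. Table 1 also continues FQ blood sampling after Day 28, so the protocol expects drug to be of interest beyond the last scheduled liver test.

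**Working it through.** No sample size, power or error rate is involved. The check compares sections and uses simple day arithmetic.

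**1. Is there a scheduled ALT at Day 63?**

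- Age >5 years: last scheduled laboratory test at V13, Day 28 ± 2 (Section 10.1.6, Table 1).
- Age ≤5 years: last scheduled laboratory test at V13, Day 28 ± 2 (Section 10.1.6).
- End-of-study visit: V15, Day 63 ± 3, with no laboratory safety test listed.

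Nominal gap: 63 − 28 = 35 days. With the visit windows, the shortest gap is 60 − 30 = 30 days and the longest is 66 − 26 = 40 days. As a share of the 63-day window: 35/63 = 56%. This is a statement about visit spacing, not a count of missed events.

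One caveat on Table 1: in the text version, the last mark in the ≤5 years laboratory row falls one column late, under Day 42. The pregnancy-test row is displaced in the same way, although Section 10.1.6 puts that test at Days 28 and 63. I therefore take Day 28 from Section 10.1.6. Even if Day 42 were right for young children, there would still be no Day 63 value and a gap of 63 − 42 = 21 days.

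Early withdrawal does not supply the missing value. Section 10.3.5 uses the end-of-study procedures, which contain no chemistry.

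**2. Who is covered by another rule?**

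- ALT >3 ULN: Appendix D repeats liver tests until normal, baseline or clinical resolution.
- ALT at AESI level: it is an adverse event, so Section 10.4.2 requires follow-up until results are normal or progression has stabilised, beyond the last planned visit if needed.
- ALT above normal but below both thresholds: Section 10.4.2 records a laboratory abnormality as an adverse event only if it is symptomatic, needs treatment or consultation, affects dosing, is serious or is an AESI. A symptom-free patient with normal baseline and ALT between ULN and 3 ULN at Day 28 normally meets none of these.
- First rise after Day 28 without symptoms: no scheduled test would show it.

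The last two groups are the actual gap.

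**3. Does the recovery table fit a single dose?**

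Entry is by peak elevation: from 3 x ULN for ALT and AST, and from 1.5 x ULN for alkaline phosphatase and total bilirubin. The classes are "never normalized, normalized after permanent discontinuation of study drug".

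- Fully dosed, elevated, later normal: not the first class, because the test normalised. Not the second, because Section 10.3.2 ties permanent discontinuation to an incomplete dose. No class is available.
- Fully dosed, elevated, still elevated when followed up: the first class is correct.
- Incomplete dose, later normal: the second class is available.
- AST, alkaline phosphatase or bilirubin above its entry threshold, no ALT trigger, still raised at Day 28 and not retested: falls into the first class by default, although recovery was never looked for. The hepatic AESI and Appendix D monitoring are triggered by ALT, so a retest is not assured.

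**The case against.** The strongest reply is that the Day 63 sentence directly follows the one sending ALT >3 ULN to Appendix D. Read in place, it tells sites to carry on past study end for patients already under that monitoring, who do have unscheduled values. This stands in part: the rule can operate for them. But the sentence is not limited to them, and read that way it adds little to Appendix D, which already runs until normal, baseline or clinical resolution.

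It can also be said that leaving ALT between ULN and 3 ULN without a dedicated rule is a clinical choice, and that labels in a descriptive table can be settled in the SAP. The first part is fair, and the schedule and threshold are for the sponsor. The second does not remove the point: the protocol has fixed two classes, and they do not fit its own regimen.

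Three stronger inferences are tempting and not supported:

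- *Every patient above ULN at Day 28 would be counted as never normalised.* The ALT part of the table starts at 3 x ULN, and return to baseline counts as recovery. Criterion E 08 admits ALT up to 2 ULN, so some patients above ULN at Day 28 are already recovered by definition.
- *Unresolved large ALT rises are lost.* Once detected, they are followed under Appendix D and Section 10.4.2.
- *Running the on-treatment window to Day 63 is itself wrong.* It is one window for all safety data, and Section 11.4.4.2 already includes unplanned and rechecked laboratory values.

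**Conclusion.** The point holds in a limited form. The Day 63 ALT rule has no scheduled measurement behind it in any of the four cohorts, with a nominal 35 days (30 to 40 with visit windows) between the last scheduled chemistry and the end-of-study visit. What can go unobserved is a new symptom-free rise after Day 28, and the later course of a Day 28 value that is raised but below the AESI and >3 ULN thresholds.

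The recovery table has no class for normalisation after a completed single dose. It can also overstate non-recovery for AST, alkaline phosphatase or bilirubin rises that had no ALT trigger and were not retested after Day 28.

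The documents give no rate of late or sub-threshold rises, so the number of patients affected cannot be estimated. The conclusion assumes that Section 10.1.6 states the laboratory schedule correctly. No efficacy analysis is affected.

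**What to change.** - Reconcile Section 10.4.1.4 with Table 1 and Section 10.1.6, so that the ALT follow-up rule and the laboratory schedule refer to the same measurements. If the rule is meant only for patients already under unscheduled monitoring, say so. Which schedule and which follow-up rule apply is for the sponsor to decide.
- In Section 11.4.4, replace the two recovery classes with *normalised (day of first normal or baseline value)* and *not normalised at last available test (day of that test)*. The day of the last test lets a reader tell persistent elevation from absence of a retest.

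The second change is table wording and programming and needs no new data. The first costs an amendment to the text; any cost beyond that depends on how the sponsor reconciles the sections.
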